Endpoint	The primary outcome will be the percentage of swallows with aspiration and/or penetration for cold milk compared with room temp milk (a total of 15 swallows will be assessed by VFSS and FEES). Based on our preliminary results, we expect to find a significant decrease in penetration and aspiration during the initial cold swallows (5 swallows). We expect this improvement to be sustained on the subsequent cold swallows (10 swallows) following the 15-minute cold liquid feeding. A decrease of 30% in penetration and/or aspiration with cold milk will be considered significant. Similarly, a 30% improvement of feeding coordination as assessed by nFant device will be considered significant.
	2. Evaluate the safety of feeding cold milk in preterm infants. We will evaluate whether cold milk will cause hypothermia (assessed by measuring Axillary temperatures), change in vital signs (respiratory rate, heart rate, and oxygen saturation) as well as change in mesenteric blood flow indices (assessed by abdominal ultrasound) These changes with cold milk feeding will be expressed as % change compared to base line (room temp milk).
Study Duration	2 years
Participant Duration	The subjects will participate in the study for approximately 48 hours during their NICU hospital stay
Population	Preterm Infants less than 34 weeks gestation admitted to NYU- Langone Long Island Hospital NICU. (n=42)
Study Sites	NYU- Langone Long Island Hospital
Number of participants	42

1. Introduction, Background Information and Scientific Rationale

Approximately half a million preterm infants are born every year in the USA.^{1,2} It is estimated that 30-70% of very low birth weight (VLBW) preterm infants will be diagnosed with swallowing dysfunction (dysphagia), with an inverse relationship between the severity of dysphagia and gestational age (GA).³⁻⁶ Although the pathophysiology of dysphagia is multifactorial,^{4,7-9} the discoordination between swallowing and breathing is the most prevalent cause of dysphagia in preterm infants,¹⁰ which often leads to airway compromise in the form of laryngeal penetration and/or tracheal aspiration into the lungs.^{7,11} Chronic airway compromise results in a persistent inflammatory state, with disease progression to chronic lung injury and *bronchopulmonary dysplasia (BPD)* that can be devastating for already fragile and developmentally immature lungs in preterm infants.^{4,7}

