- The axillary temperature will be measured immediately prior to and after each feeding condition. It will also be measured at 10, and 30 minutes after the CS feed, at the same time the gastric content temperatures are taken. Infants' vital signs will be recorded (blood pressure, respiratory rate, heart rate, and oxygen saturation), as well as evidence of bronchospasm, lethargy, respiratory distress, apnea, tachypnea, cyanosis, bradycardia, or tachycardia.
- Doppler ultrasound (Sonosite Edge Ultrasound system, Sonosite, Inc, WA) will be used to measure
 intestinal blood flow indices including the superior mesenteric artery flow (SMA), peak systolic velocity,
 SMA mean velocity, SMA end-diastolic velocity, resistive index, pulsatility index, portal vein volumetric
 blood flow, as well as heart rate and mean arterial blood pressure. Intestinal blood flow monitoring via
 Doppler ultrasound will be performed 6 times for each participant, performed one hour before and at 30 and
 60 minutes after both bedside feeding conditions (RTS and CS). Measurements will be taken at the bedside
 in the supine position.
- Step 2 (done 24-48 hours after step 1):
 - Infants will be transported to the radiology suite and undergo VFSS and or FEES, as ordered by the treating
 medical team (Figure1: the blue boxes indicate procedures done for research purpose only. None of the
 research procedures are experimental and are approved tests for neonates including VFSS, FEES, nfant
 test and abdominal ultrasound).
 - Routine procedure for VFSS or FEES will be followed as ordered by the medical team. This procedure is part of the routine clinical care and not considered part of the research study.
 - If no dysfunction is noted, the procedure will end, and the child will no longer be eligible for further participation in this research study. If dysfunction (penetration/aspiration) either on the VFSS or FEES study is noted, the child will be eligible to participate in the next phase of the study.
 - Immediately following the initial VFSS-FEES assessment, the infants will remain in the same seated position with the FEES scope in place. While keeping all variables from the standard VFSS-FEES the same, the infant will be fed cold barium (4-9°C) using the same nipple. A total of 5 swallows will be visualized using VFSS and FEES, labeled "Cold Swallows-1 (CS1)." These 5 swallows assessment are done for the research purpose only.

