Axillary temperatures, as well as mesenteric blood flow indices, will be compared between the CS and RTS feeds. A Two One-Sided Test (TOST) will be used to evaluate whether the body temperature and blood flow indices are equivalent before and after the cold liquid swallow. Equivalence will be determined if the 90% confidence interval of pre-post change is contained within the predefined margin of ± 0.5 . *Power and sample size:* The study subjects are the same subjects enrolled in Aim 1 (n=42). We have simulated data assuming a margin of equivalence from - 0.5° C to 0.5° C, significance level 0.05, TOST and 10000 Monte Carlo samples. With the planned sample size for aim 1 (N=42), we will have sufficient power (>80%) to detect equivalence when the margin of equivalence is from - 0.5° C to 0.5° C and the actual mean difference is zero.

5. Study Enrollment

Inclusion Criteria

 Viable preterm infants less than 34 weeks gestation), 2) admitted to NYU- Langone Long Island Hospital NICU, 3) PMA > 35 weeks at the time of the study, 4) receiving no or minimum respiratory support (<2 lit/min low-flow nasal cannula), 5) tolerating at least 50% of their enteral feeding orally and 6) having symptoms of swallowing dysfunction during oral feeding (clinical dysphagia). 7) referred by the medical team for VFSS and/or FEES assessments.

Exclusion Criteria

Exclusion criteria include children with other comorbidities, such as IUGR, upper airway anomalies, brain injury, neuromuscular disease, or life-threatening congenital disease.

Total Number of Participants and Sites

We will need 42 subjects over a 2 years period.

Vulnerable Subjects

Our population will include children by nature of the study objectives.

The study has potentially greater than minimal risk, but there is possible direct benefit to the individual subject. Although previous studies as well as our preliminary study didn't show any evidence of cold stress in response to cold milk feeding, it is a potential risk. In addition there will be minor increase in radiation exposure as described previously. Currently there is no effective treatment for dysphagia in preterm infants. The results of this research (the safety and effectiveness of cold milk for each subject) will be disclosed to the medical team. If the results confirm safety and efficacy for that infant, the medical team can consider using cold milk to treat the infant's dysphagia which can be a significant benefit to the subject.

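### The synopsis puts safety changes on a % scale relative to the room-temperature feed, while the statistics section tests pre-post change within ±0.5; scale and baseline need to be made the same, with one scale per measure

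*Combined protocol and SAP*

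**What the plan says.** Two places in the combined protocol and SAP describe how the safety measures are handled.

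- **Synopsis, Endpoint, item 2.** After naming axillary temperature, vital signs and mesenteric flow indices, it says: "These changes with cold milk feeding will be expressed as % change compared to base line (room temp milk"). The baseline here is the room-temperature (RTS) feed, and one scale serves every measure. It does not say whether individual % changes are summarised by a mean, a median or a ratio of means.
- **Section 4, Statistical Considerations, item 2 (safety).** It opens with "Axillary temperatures, as well as mesenteric blood flow indices, will be compared between the CS and RTS feeds", without naming a scale. It continues: "A Two One-Sided Test (TOST) will be used to evaluate whether the body temperature and blood flow indices are equivalent", and the comparison is now before against after the cold swallow. The rule is: "Equivalence will be determined if the 90% confidence interval of pre-post change is contained within the predefined margin of" ±0.5, with no unit. The unit appears only in the power statement: "We have simulated data assuming a margin of equivalence from - 0.5° C to 0.5° C, significance level 0.05".

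The measures covered differ in kind. Step 1 of Section 4 lists, besides superior mesenteric artery (SMA) peak systolic velocity, "SMA mean velocity, SMA end-diastolic velocity, resistive index, pulsatility index, portal vein volumetric" blood flow. On timing, "Doppler ultrasound will be performed 6 times for each participant, performed one hour before and at 30 and" 60 minutes after each of the RTS and cold (CS) feeds. Either baseline can therefore be formed from the data.

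**The concern.** An analyst following the synopsis would compute, for each infant, the cold reading divided by the room-temperature reading, minus one. An analyst following the statistics section would compute the reading after the cold feed minus the reading before it and set its interval against ±0.5. These are different quantities on different scales with different reference points. A pre-post change within the cold feed also contains whatever feeding itself does; a CS-versus-RTS contrast is aimed at temperature alone.

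For the flow indices, % change is the only scale the documents name. The ±0.5 margin has a unit that fits temperature only, so it gives no usable equivalence criterion for a velocity, a volumetric flow or a dimensionless index.

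The % scale also has a statistical defect when individual values are averaged: the denominator is a noisy reading, so the average ratio exceeds the true ratio. A lack of adverse effect on intestinal blood flow is a stated hypothesis of the study. An upward shift in velocity or flow ratios leans towards reassurance.

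**Working it through.** **1. The plan's own figure.** The safety paragraph states: "With the planned sample size for aim 1 (N=42), we will have sufficient power (>80%) to detect equivalence" for ±0.5 °C with a true difference of zero. No SD is given, so the figure cannot be reproduced exactly. A simulated paired TOST (90% t-interval inside ±0.5, N=42) gives 88% power at an SD of change of 1.0 °C, 79% at 1.1 and 69% at 1.2. The claim therefore holds for any SD up to about 1.09 °C. This calculation is in degrees and says nothing about a % scale or the Doppler indices.

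**2. The two places side by side.**

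| | Synopsis, Endpoint item 2 | Statistical Considerations, item 2 |
|---|---|---|
| Scale | % change | change, within ±0.5 |
| Baseline | RTS feed | before the cold swallow (TOST); RTS feed (opening sentence) |
| Unit for temperature | % | °C (power statement only) |
| Unit for flow indices | % | none |

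The unit makes a difference. At 36.5 °C, ±0.5 °C is 0.5/36.5 = ±1.37%. Read as percentage points, ±0.5% of 36.5 °C would be 0.005 × 36.5 = ±0.18 °C.

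**3. Bias of an averaged % change.** Let C and R be an infant's cold and room-temperature readings, with no true effect. Take lognormal repeat errors with coefficient of variation CV, independent between the two readings. The infant's own level cancels in the ratio, leaving E[C/R] = E[C] × E[1/R] = 1 + CV². The expected mean % change is therefore CV², not zero. If the true ratio is 0.9, the expected value is 0.9 × (1 + CV²) − 1.

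| Within-infant CV (assumed) | Expected mean under no effect | A true 10% fall reads as |
|---|---|---|
| 10% | +1.0% | −9.1% |
| 20% | +4.0% | −6.4% |
| 30% | +9.0% | −1.9% |

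If CV instead means the total spread across infants and the two readings correlate at ρ, the bias is (1 + CV²)^(1−ρ) − 1. At ρ = 0.5 this is +0.5%, +2.0% and +4.4% for the same three CVs.

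If ±0.5 were taken as percentage points for a flow index, the bias alone would fill the margin at CV = √0.005, about 7%.

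**4. Other summaries.** Simulation used n=42, a true 10% fall, total CV 20% or 30%, and ρ 0.2 or 0.5. At ρ = 0.2 the mean % change was −7.1% (CV 20%) and −3.6% (CV 30%). The median % change, ratio of means and geometric mean ratio each returned about −10% in all four cases.

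**5. Direction.** The shift is upward for every index. For SMA velocities and portal flow it makes a fall look smaller. For resistive and pulsatility indices it makes a rise look larger.

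**6. Temperature.** With an assumed SD of 0.3 °C around 36.7 °C, CV = 0.3/36.7 = 0.8%. The bias is then about 0.005% (ρ = 0.2), and % change correlates 0.9999 with the °C difference. The percentage does depend on the unit: 0.5 °C at 36.5 °C is 1.37% in Celsius, but 0.9/97.7 = 0.92% in Fahrenheit.

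**The case against.** The strongest reply is that the synopsis sentence is descriptive and the inference lies elsewhere. For temperature that largely stands: the powered TOST margin is in °C, and hypothermia is an absolute threshold (below 35.5 °C, in the adverse event definitions), so no stated decision rests on a percentage. For flow it does not stand, because the statistics section names no scale and its margin has no applicable unit.

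The second reply is that the bias is conditional. It needs individual % changes to be averaged arithmetically, which the plan does not say, and its size rests on CVs the documents do not give. That is correct. At CV 10% the bias is at most 1%, and averaging the 30- and 60-minute scans would roughly halve it if their errors are independent.

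A reader might infer that the plan will hide a fall in intestinal flow. The documents do not support that: neither the summary nor the noise level is stated, and for resistive and pulsatility indices the shift exaggerates an apparent rise. A reader might also infer that % change makes the temperature result meaningless. It does not; over the body-temperature range it is almost an exact rescaling of the °C difference. Nor do the documents suggest that zero readings are expected. A zero baseline would leave a % change undefined, but that is a precaution for the analysis rules and no observed fault.

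**Conclusion.** The point holds as an inconsistency with a conditional statistical consequence. What can be checked from the text alone is that the synopsis and the statistics section disagree on scale and baseline, and that ±0.5 has no unit for the flow indices. The consequence is an upward bias of about CV² in a mean of individual % changes: about +1%, +4% and +9% at within-infant CVs of 10%, 20% and 30%. It rests on arithmetic averaging, independent lognormal repeat errors and assumed CVs, and it is smaller if the CV is a total CV and the readings are correlated. For temperature the issue is one of unit and readability against the °C margin, with no material bias. This is a low-severity point: an improvement that costs no data and does not overturn the safety analysis.

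**What to change.** Replace the % change sentence in the synopsis with one scale per measure, and use the same wording under Statistical Considerations:

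- **Axillary temperature:** CS minus RTS difference in °C, with 90% CI, read against the plan's existing ±0.5 °C margin.
- **Flow, velocity and resistance indices:** within-infant log ratio, reported as the geometric mean ratio CS:RTS with 90% CI. Use the plain difference for any index that can be zero.
- **Equivalence margin for flow:** state it on the same scale as the estimate. The clinical investigators need to choose and justify its value.
- **Baseline:** use the same one in both places. If the pre-feed scan is used as well, say how it enters, and say which post-feed scan (30 minutes, 60 minutes or their average) is analysed.
- **Vital signs:** the same synopsis sentence covers them, so name their scale too.

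The cost is a wording amendment before analysis. The six scans and the temperature readings already planned supply everything needed.

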This will be a prospective study, with each infant serving as their own control. All study subjects will meet the inclusion/exclusion criteria listed in Section 5 of this proposal and informed consent will be obtained. The subject will be considered for the study if the medical team diagnosed the infant with clinical dysphagia and decided to obtain Video Fluoroscopic Swallow Study (VFSS), or Fiberoptic Endoscopic Evaluation of Swallowing [FEES) or both to help manage the dysphagia (such as delay oral feeding till the child is more mature or use feeds thickeners). The VFSS and FEES are not a requirement for step 1 however abnormal VFSS and FEES are requirement for step 2.

The following study procedures will be done before the routine VFSS/FEES testing ordered by the medical team:

Study Protocol Timeline

• Step 1 (bedside procedures):

- We will evaluate the infant's sucking, swallowing, and breathing patterns using a non-invasive FDA approved equipment (nFant® Feeding Solution). This device is in clinical use for several years and routinely used in several NICUs. The nFant has a wireless sensor within the nipple to assess sucking and swallowing coordination during feeding. This machine is not routinely used in NYU- Langone Long Island Hospital NICU because of costs but will be available only for infants enrolled in this research study. The nfant assessments will be performed by the research team under two separate feeding conditions, standard room temperature (RTS) and cold temperature (CS, at 4-9°C) of milk/formula for an entire feeding (15-20 minutes). The two feedings will be done on the same day but may not necessarily be two consecutive feedings (depending on the baby's eagerness to feed orally). The order of each condition will be randomized to control for fatigue. Inter- and intra-rater reliability measures will be calculated. The nfant assessments will include the following measurements:
 - peak amplitude the displacement of the nipple during compression phase normalized from a calibrated 0% to 100%;
 - duration how long or drawn out sucking events are from onset to end in seconds;

- frequency the rate at which consecutive suck events are occurring in Hertz;
- > suck bursts number of sucks per burst, duration and number of bursts, and active time spent sucking;
- > suck smoothness the number of velocity changes in a nipple amplitude trace during a suck.

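### The Step 1 equivalence test rests on raw change around the cold feed and uses neither the room-temperature control feed nor the randomised feed order

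*Combined protocol and SAP*

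**What the plan says.** Section 4, Study Design, Step 1 describes two bedside feeds per infant, one at room temperature (RTS) and one cold (CS). On timing: "The two feedings will be done on the same day but may not necessarily be two consecutive feedings". On order: "The order of each condition will be randomized to control for fatigue". Neither the allocation method nor any blocking is given.

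Each feed has its own baseline. For temperature: "The axillary temperature will be measured immediately prior to and after each feeding condition". Doppler is done one hour before, and 30 and 60 minutes after, both feeds. Further axillary readings at 10 and 30 minutes are scheduled after the cold feed only.

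The safety part of Statistical Considerations opens with a between-feed comparison: "Axillary temperatures, as well as mesenteric blood flow indices, will be compared between the CS and RTS feeds". The test that follows asks whether values are "equivalent before and after the cold liquid swallow", and equivalence requires that the "90% confidence interval of pre-post change is contained within the predefined margin of ± 0.5". The Endpoint entry of the synopsis gives a third form, a percentage change relative to the room-temperature condition.

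For nFant, the measurement described alongside the randomisation, the synopsis gives only a threshold: "a 30% improvement of feeding coordination as assessed by nFant device will be considered significant". No test, model or interval is stated.

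**The concern.** The design collects what a crossover analysis needs: a control feed, a randomised order and a baseline in each period. The equivalence test uses only the cold feed's pre and post readings.

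Two consequences follow. First, write the change around a feed as c + k, where c is whatever change accompanies any feed and k is the part due to cold. The stated test examines c + k. The comparison announced in the preceding sentence concerns k, and only the room-temperature feed can separate the two. Second, if the between-feed comparison is made without a period term, any difference between first and second feeds stays in the error. If the order counts are unequal, it also moves the estimate. At stake is whether the 90% CI for temperature or a Doppler index falls inside the margin, and what an equivalence conclusion would mean.

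**Working it through.** **Inputs from the documents.** N = 42, margin ±0.5 °C, significance level 0.05, true difference zero, claimed power above 80% (Statistical Considerations, safety aim). No SD, period effect or correlation is given for any Step 1 outcome. The pre-post correlation of 0.20 in the sample-size text belongs to aspiration and penetration in Step 2.

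**The plan's own figure.** Without an SD, the >80% cannot be reproduced directly. Simulated paired TOST power at N = 42, by assumed SD of the quantity tested:

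| SD (°C) | 0.5 | 0.8 | 1.0 | 1.08 | 1.1 | 1.2 |
|---|---|---|---|---|---|---|
| Power | 100% | 98% | 88% | 81% | 79% | 69% |

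The claim is met for any SD up to about 1.08 °C.

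**Effect of a period term on a cold-minus-room difference.** Let d be the within-infant difference, τ the cold effect, π the second-minus-first feed effect on the scale analysed, and σ the SD of d within an order group. Then d = τ + π + error if cold is second, and d = τ − π + error if cold is first.

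- Ignoring order at 21:21, the variance of d is σ² + π². At π = 0.5σ this is 1.25σ², a 25% inflation (42/1.25 = 33.6, so 42 infants count as about 34).
- Adjusting for order, the estimate is the average of the two order-group means, with variance (σ²/4)(1/n₁ + 1/n₂). At 21:21 this is σ²/42. At 26:16 it is 0.02524σ² against 0.02381σ², so with no period effect the CI is √1.06 ≈ 1.03 times as wide.

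Ratio of adjusted to unadjusted 90% CI width, and TOST power (unadjusted → adjusted) at an assumed σ of 1.0 °C:

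| π/σ | Width, 21:21 | Width, 26:16 | Power, 21:21 | Power, 26:16 |
|---|---|---|---|---|
| 0 | 1.00 | 1.03 | 87.7 → 87.6% | 87.6 → 85.3% |
| 0.2 | 0.98 | 1.01 | 87.0 → 87.9% | 85.0 → 85.2% |
| 0.5 | 0.89 | 0.925 | 81.8 → 87.6% | 70.3 → 85.0% |

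At σ = 0.5 °C, power is at least 99% in every scenario run.

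**Order imbalance.** The unadjusted estimate shifts by π(n₁ − n₂)/N: zero at 21:21 and (10/42)π = 0.24π at 26:16. If order were allocated by simple randomisation, 26:16 or worse would occur 16% of the time. The imbalance fraction then has SD 1/√42 = 0.154, so the shift has variance π²/42. That is the same extra variance as above, so the two must not be counted as separate harms.

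**What change scores already remove.** If the second feed starts and ends higher by the same amount, pre and post readings both carry it and subtraction cancels it. For change scores, π is only the part by which the feed-related change itself differs between first and second feeds.

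**Baseline adjustment.** Infant-level effects cancel in a crossover. The gain from adjusting for the pre-feed value, rather than subtracting it, therefore depends on the correlation between the pre-feed and post-feed between-feed differences. The documents give nothing from which to estimate this, so no figure is offered.

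**The case against.** The best defence is that the TOST as written asks a legitimate question: does the infant's temperature or blood flow move around a cold feed? On that reading there is no between-feed contrast to adjust, and change scores already remove an additive order effect. Randomisation keeps an unadjusted between-feed mean unbiased on average. Randomising against fatigue is a precaution: the protocol gives no size for it, allows non-consecutive feeds, and does not link fatigue to axillary temperature or mesenteric flow. With a small SD, nothing changes.

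Much of this stands, and it limits the claim. It does not explain why the same paragraph announces a cold-versus-room comparison, and the synopsis expresses change relative to room-temperature milk, while the decision rule uses neither.

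Four stronger readings are tempting and are not supported:

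- That the equivalence intervals are known to be too wide, or the result biased by order. Both depend on an undocumented period effect, and the stated test is not a between-feed interval.
- That the nFant analysis ignores order. No nFant analysis is stated; the gap is a missing method.
- That baseline adjustment would save a calculable share of variance through the parallel-group ratio (1 + ρ)/2 with the ordinary pre-post correlation. That is the wrong correlation for a crossover.
- That the efficacy conclusion is affected. The primary outcome comes from Step 2, where the standard study always precedes the cold swallows and order is not randomised.

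**Conclusion.** The point holds as a mismatch between design and analysis in Step 1. The equivalence rule leaves out the control feed, the randomised order and any adjustment for the pre-feed reading, although all the data are collected. The contrast is also left undefined between three forms.

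The size is conditional. For a cold-minus-room difference with balanced order, a period term changes CI width by about 2% or less when the period effect is 0.2 SD or smaller, and removes about 25% variance inflation at 0.5 SD. A material effect on the temperature TOST needs a period effect near 0.5 SD together with an SD near 1 °C; neither is documented. The case for change rests on its low cost and on making the test answer the stated comparison, not on a demonstrated loss of power.

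**What to change.** - Define the Step 1 safety contrast as cold minus room temperature, and name the post-feed time. For temperature, only the reading immediately after the feed exists for both conditions; the 10- and 30-minute readings have no room-temperature counterpart. Doppler has 30 and 60 minutes for both.
- For temperature and each Doppler index, model the post-feed value on condition, period and that period's pre-feed value, with infant as random effect. Take the 90% CI for the TOST from this model. Change around the cold feed can still be reported descriptively.
- For nFant, use the same model without a pre-feed term and report a 95% CI beside the 30% threshold.
- Allocate feed order 1:1 in permuted blocks, and say so.
- Restate the TOST power for this contrast with its assumed SD. If changes at the two feeds have equal SD s and correlation r, their difference has SD s√(2(1 − r)), which exceeds s when r is below 0.5.

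The cost is SAP wording, a blocked order list, and one degree of freedom each for period and baseline. With a 26:16 split and no period effect, the CI would be about 3% wider; blocking largely avoids this. No new measurements are needed.
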